7.1.3 Smears Processing and Transport

- 1. Label the slide with a random number sticker.
- 2. For the thick blood smear:
 - a. Place a drop of blood in the center (1 cm from the edge of the slide) of a clean, dust-free, and grease-free slide.
 - b. Spread the drop of blood evenly with a disposable wooden applicator or with another clean slide into a circle with a diameter of 1 cm.
 - c. The blood smear should be about 1cm away from the edge of the slide. The correct thickness of a thick blood smear is one through which newsprint is barely visible when the blood is still wet.
- 3. For the thin blood smear:
 - a. Place a smaller drop of blood on the slide.
 - b. Using another slide angled at 45°, create a feathered edge before reaching the other end of the slide.
- 4. Allow the blood smears to air dry flat. Do not heat the slides, as this will damage the parasites. Be sure to protect the slide from dust and insects. Do not refrigerate slides, as this may cause the smears to detach from the slide during the staining procedure.
- 5. When dry, place the thick and thin blood smears into the slide box.

- 6. Smears will be transported at room temperature each day to a diagnostic facility near the study area.
- Within 24 hours of thick and thin blood smear collection, the smears will be stained with 2% Giemsa stain for 30 minutes. (The thin smear will be fixed by submerging it in 100% methanol for 30 seconds and then let it air dry for 1-2 minutes prior to the Giemsa stain.)
- 8. Parasite density will be measured by a masked reader using a microscope at the diagnostic facility.

Smears will be stored at room temperature.

7.1.4 Thick and Thin Blood Smears Materials

Glass slides Slide box Rolls of random number stickers

8.2 Measuring Body Temperature

Measuring temperature:

Place a clean lens filter (cover) over the end of the device. Press the Start button and push the «I/O» button to clear the previous reading. During the internal self-check, the display shows all segments. Then the last temperature taken will be displayed together with «MEM». Wait for the ready signal to beep and the ready symbol in the display. Fit the probe snuggly into the canal of the child's right ear, then push and release the Start button. If the probe has been securely inserted into the ear canal during the complete measuring process, a long beep will signal the end of the measuring process. The thermometer detects that an accurate temperature measurement has been taken. The result is shown on the display.

If the probe has not been constantly placed in a stable position in the ear canal, a sequence of short beeps will sound, the «ExacTemp» light will go out and the display will show an error message («POS» = position error).

For the next measurement, eject the used lens filter (push the ejector) and put on a new, clean lens filter. Clear the display by pushing the «I/O» button once. Wait for the ready signal. Fit the probe snuggly into the ear canal, then push and release the Start button

The ear thermometer turns off automatically after 60 seconds of inactivity. The device can also be turned off by pressing the «i/O» button for at least three seconds.

Collect used lens filters to be cleaned at the end of the day.

8.3 Venipuncture Blood Draw

Protection of Examiner and Study Participant

Prior to examinations at the blood station and the swab station, the examiner and tuber must be gloved. The examiner will put latex gloves on both of his/her hands prior to touching the participant and a new pair of gloves will be used for each participant in order to avoid transmitting infection between participants. Purell® Instant Hand Sanitizer will be available for hand sanitization when needed.

It is important to handle all blood specimens with care

to minimize risk of infection

Wear gloves. New gloves must be worn for each child.

Clean spills. In the event of a blood spill or splash, clean immediately with approved disinfectant (10% bleach or chlorhexidine solution) and wipe with absorbent material.

Disposal of sharps. All lancets must be disposed of properly in sharps containers.

No food. Food and drink are not allowed at the blood collection station.

Determination of the maximum allowable blood draw volume

See the chart below in order to determine the maximum allowable blood draw volume from children and infants, based on body weight.

Body wt in kg	Max drawn in one blood draw
	2.5% of total blood volume
1 kg	2.5 ml
2 kg	4.5 ml
3 kg	6 ml
4 kg	8 ml
5 kg	10 ml
6 kg	12 ml
7 kg	14 ml
8 kg	16 ml

9 kg	18 ml
10 kg	20 ml
11 thru 15 kg	22 - 30 ml
16 thru 20 kg	32 - 40 ml
21 thru 25 kg	42 - 50 ml
26 thru 30 kg	52 - 60 ml
31 thru 35 kg	62 - 70 ml
36 thru 40 kg	72 - 80 ml
41 thru 45 kg	82 - 90 ml
46 thru 50 kg	92 - 100 ml
Greater than 50 kg	100 ml

Citation for above chart: Seattle Children's Hospital Powered by Mayo Medical Laboratories. "Maximum Allowable Blood Draw from Infants." https://seattlechildrenslab.testcatalog.org/show/1000721-1

Cell-Free Plasma extraction

In order to prepare whole blood for downstream molecular biology techniques, plasma with an absence of lysed blood cells must be prepared from the whole blood. Plasma is prepared as follows, according to the Streck tube protocols.

- 1- Centrifuge whole blood at 1,600 x g for 10 minutes at room temperature (20-25°C).
- Carefully pipette the upper plasma layer without disturbing the lower blood cell layer or pipetting up any red material. Transfer the plasma to a separate conical-bottom tube.
 *Discard the remaining blood cells and tube in Biohazardous Waste.
- 3- Centrifuge the plasma at 16,000 x g for 10 minutes.
- 4- Carefully pipette the upper plasma layer (translucent), avoiding the opaque lower layer, and aliquot it into labeled cryo-tubes, with 200uL in each tube.
 *Discard the remaining fluid and tube in Biohazardous Waste.
- 5- Store extracted plasma at \leq -80°C for future use in molecular biology protocols.

7.2.1 Blood Draw Protocol

Identification

Identify the child by scanning her/his study identity card.

[figure not shown]
Verify the identity of the child with the mother/guardian of the child: check the name, study identification number, sex, age and the name of the mother and father of the child.

Supplies 2 chairs 1 examination table pillow
 Cotton ball
 Alcohol wipes
 Wing needle 23G with tubing and holder
 needle container
 trash bag
 small bandage
 pair of gloves
 tube to collect blood (streck brand Cell Free DNA tubes)
 tourniquet
 tablet
 unique identification number
 blue pad to put under the arm of the child

Immobilization

Ask if the mom/guardian of the child would like to help by holding the child. If the parent accepts to hold the child, provide full instructions:

- Stand on opposite side of the table
- Ask the person holding the child to:
 - Stretch an arm across the table and place the child on its back, with its head on top of the outstretch arm
 - Pull the child close, as if you were cradling with the child
 - Grasp the child's elbow in the outstretched hand
 - Use your other arm to reach across the child and grasp its wrist in a palm up position (reaching across the child anchors the child's shoulder, and thus prevents twisting and rocking movements)

Immobilize the baby or child.

- If the child can sit on its own:
 - Sit the child on your lap, facing the examiner
 - Hold the legs of the child between your legs
 - Extend the child's arm and grasp the child's elbow
 - With your other hand grasp the child's wrist in a palm up position

Use the pillow to make the child more comfortable or to hold is elbow. Comfort is very important for the child to feel safe.

Explaining the person who is helping you how to hold the child is very important, make sure the person understands what you need from him/her

[figure not shown]
Reassure the child, talk to the child with a calm voice, and touch the child gently

Procedure

- 1. Collect supplies and equipment
- 2. Wash your hands
- 3. Look at the arms of the child to try to find a good venipuncture site
- 4. Wash your hands
- 5. Immobilize the child
- 6. Put the tourniquet on the child about 2 fingers widths above the venipuncture site chosen
- 7. Put on your gloves
- 8. Attach the end of the tubing to the end of the holder
- 9. Remove the plastic sleeve from the needle
- 10. Using the alcohol swab, disinfect the venipuncture site and allow it to dry
- 11. Draw the skin using your tumb and stick the needle in the vein
- 12. Push the tube onto the holder until the needle is in it
- 13. Blood should begin to flow into the tube
- 14. Fill the tube until it is full, remove the tube
- 15. Release the tourniquet
- 16. Place a dry coton ball over the venipuncture site and withdraw the needle
- 17. Ask the parent/guardian to continue applying mild pressure
- 18. Dispose of the needle in the sharps container
- 19. Dispose of all contaminated supplies in the trash
- 20. Label the tube with a label containing a unique number
- 21. Put a bandage on the child's arm and ask the mom to remove it 1h later
- 22. Gently and completely invert the tube 10 times in order ro mix blood with the tube preservation agents
- 23. Remove gloves, put them in the trash
- 24. Wash your hands

Illustrations

[figure not shown]
- Use a winged steel needle, usually 23 or 25 gauge, with an extension tube (butterfly). Keep the tube and needle separate until the needle is in the vein.
- 2. Collect supplies and equipment.
- Perform hand hygiene (if using soap and water, dry hands with single-use towels).

15. Place dry gauze over the venepuncture site and slowly withdraw the needle.

[figure not shown]

18. Dispose of the butterfly in a sharps container.

[figure not shown]

16. Ask the parent to continue applying mild pressure.

[figure not shown]
19. Properly dispose of all contaminated supplies.

[figure not shown]
- 21. Put an adhesive bandage on the patient if necessary.
- 22. Remove gloves, dispose of them appropriately and perform hand hygiene (if using soap and water, dry hands with single-use towels).

17. Remove the butterfly from the vacuum tube holder.

20. Label the tube with the patient identification number and date.

4. Immobilize the baby or child.

6. Put on well-fitting, non-sterile gloves.

 Disinfect the collection site and allow to dry.

12. Blood should begin to flow into the tube. 13. Fill the tube until it is full or until the vacuum is exhausted; if

[figure not shown]
 Attach the end of the winged infusion set to the end of the vacuum tube and insert the collection tube into the holder until the tube reaches the needle.

10. Use a thumb to draw the skin tight, about two finger widths below the venepuncture site.

13. Fill the tube until it is full or until the vacuum is exhausted; if filling multiple tubes, carefully remove the full tube and replace with another tube, taking care not to move the needle in the vein.

 Put the tourniquet on the patient about two finger widths above the venepuncture site.

8. Remove the plastic sleeve from the end of the butterfly.

11. Push the vacuum tube completely onto the needle.

14. After the required amount of blood has been collected, release the tourniquet.

Tips and Warnings

Make sure the right child is in front of you, verify his/her identity with the mom/guardian

Take your time to choose your venipuncture site. Choose the venipuncture site while the child is still in his/her mom's arm, when s/he feels safe.

Keep the child warm, it will help dilate the vein and increase the blood flow: use swaddling blanket, let the mother hold the child/infant, warm the area of puncture with warm cloths.

Ask the person helping you holding the child if they can rhythmically tighten and release the child's wrist to ensure that there is an adequate flow of blood

Let the child suck on something (pacifier, breast) during the venipuncture if needed

Distract the attention of the child away from the puncture

Do not touch the cleaned site, if the cleaned site is contaminated, repeat the disinfection

Do not let the tourniquet in place more than 2 minutes

Do not attempt the venipuncture more than 3 times

9 Chapter 9: Anthropometry

Anthropometry will be collected for all children at baseline, 14 days, and 180 days after the completion of the treatment. We will measure length or height, weight, and MUAC.

9.1 Measuring Length and Height

A lightweight measuring board will be used to measure the participant's height to the nearest 0.1 cm.

Length or Height will be assessed with a ShorrBoard. Depending on a child's age and ability to stand, measure the child's length or height.

Length: If a child is less than 2 years old, or cannot stand alone, measure recumbent length. A child's length is measured lying down (recumbent).

Height: If a child is able to stand, we will measure standing height.

8.1.1 Procedure

If the child has braids or hair ornaments that will interfere with length/height measurements, remove them if possible. Check that any sandals, shoes, or socks have also been removed.

Whether measuring length or height, the mother/guardian is needed to help with measurements and to soothe and comfort the child. Explain to the mother the reasons for the measurements, and describe the steps in the procedure. Answer any questions she might have. Show her and tell her how she can help you. Explain that it is important to keep the child still and calm to obtain the best measurement. ShorrBoard Set-Up

- 1) Remove ShorrBoard from bag.
- 2) Stand the ShorrBoard upright. You can step on the base of the board to keep it stable.
- 3) As you face the board, turn the non-removable bolt counterclockwise to release the extension piece. Note: the bolt remains attached to the back of the extension piece do NOT remove it.
- 4) Slide the extension piece into the top end of the main board and fasten the clasp on the back of the board. Make sure the clasp is fastened properly.
- 5) The auto-lock sliding head/footpiece is stored in the base of the main board and can be moved up and down the length of the measuring board. It should stay in place on its own wherever you position it.
- 6) The measuring board must be placed against a firm surface for standing height (e.g. wall, table, tree, against a vehicle, etc.). Make sure the board is stable. If necessary, place items such as small rocks underneath the height board to stabilize it during the measurement.
- 7) Clean the equipment with alcohol swabs at the beginning of each day.

Note: when you set up the board each day, examine each of the pieces to check for damage.

9.2 Measure Length

[figure not shown]
Cover the length board with a chuck for hygiene and for the baby's comfort. Explain to the mother that she will need to place the baby on the length board and then help to hold the baby's head in place while the measurement is taken. Show her where to stand when placing the baby down (i.e. opposite you, on the side of the length board away from the tape). Also show her where to place the baby's head (against the fixed headboard) so that she can move quickly and surely without distressing the baby. When the mother understands your instructions and is ready to assist: Ask her to lay the child on his back with his head against the fixed headboard, compressing the hair.

Quickly position the head so that an imaginary vertical line from the ear canal to the lower border of the eye socket is perpendicular to the board. (The child's eyes should be looking straight up.) Ask the mother to move behind the headboard and hold the head in this position.

Speed is important. Standing on the side of the length board where you can see the measuring tape and move the footboard: Check that the child lies straight along the board and does not change position. Shoulders should touch the board, and the spine should not be arched. Ask the mother to inform you if the child arches the back or moves out of position. Hold down the child's legs with the one hand and move the footboard with the other. Apply gentle pressure to the knees to straighten the legs as far as they can go without causing injury or distress.

Note: it is not possible to straighten the knees of newborns to the same degree as older children. Their knees are fragile and could be easily injured, so apply only minimum pressure.

If a child is extremely agitated and both legs cannot be held in position, measure with one leg in position. While holding the knees, pull the footboard against the child's feet. Upon reading the measurement, the examiner will clearly call out the number to the recorder. Record the child's length in centimeters to the last completed 0.1 cm. (1.0 mm). Keeping the child in place, release the sliding footboard, and prepare to repeat the measurement. Re-position the child for a second and third measurement.

[figure not shown]
9.3 Measure Standing Height

Ensure that the height board is on level ground. Working with the mother, and kneeling in order to be at the level of the child. Help the child stand on the baseboard with the weight of the child evenly distributed on both feet. The heels of the feet are placed together with both heels touching the base of the vertical board. Place the feet pointed slightly outward at a 60 degree angle. The back of the head, shoulder blades, buttocks, calves, and heels should all touch the vertical board. Arms should hang freely by the sides of the body with the palms facing the thighs.

Note: Standing with all body parts touching the board may be difficult for some children, in which case, help the child to stand on the board with one or more contact points touching the board.

Ask the mother to hold the child's knees and ankles to help keep the legs straight and feet flat, with heels and calves touching the vertical board. Ask her to focus the child's attention, soothe the child as needed, and inform you if the child moves out of position. Position the child's head so that a horizontal line from the ear canal to the lower border of the eye socket runs parallel to the baseboard. Ask the child to inhale deeply and to stand fully erect without altering the position of the heels. If necessary, push gently on the belly to help the child stand to full height.

Still keeping the head in position, use your other hand to pull down the headboard to rest firmly on top of the head and compress the hair. Upon reading the measurement, the examiner will clearly call out the number to the recorder. Record the child's height in centimeters to the last completed 0.1 cm (1.0 mm). Keeping the child in place, release the sliding headboard, and prepare to repeat the measurement. Reposition the child for a second and third measurement.

8.3.1 Dismantling the ShorrBoard

- 1) Stand the board upright: face the board and step on the base with one foot to keep it stable.
- 2) Slide the head/footpiece into the base of the main board.
- 3) Release the clasp on the back of the extension piece and remove it. Push the clasp FLAT against the extension piece.
- 4) To attach the extension piece to the main board, turn the front of the extension piece inward and place it against the front of the main board. Make sure that all sides of the extension piece are straight and in line with the main board.
- 5) Push on the bolt that is on the back of the extension piece and screw it into the main board.

6) Put the board back inside of the carrying case for storage until your next use.

9.4 Measuring Weight

The SECA 874 scale will be used to weigh infants and children to the nearest 0.01 kg. Infants and young children can also be weighed simultaneously with their parent or guardian by the unique "mother-baby" function (parent or guardian is weighed and then the infant or child is weighed while held by the parent). Explain to the mother that we want to weigh her child to see how he or she is growing. If she has a baby or a child who is unable to stand, she will hold the child on the scale. If the child is 2 years or older/can stand alone, the child will be weighed alone. Children should be wearing only light clothing, no shoes or sandals, no hair ornaments, and no jewelry. Explain that the child needs to remove outer clothing and shoes/sandals in order to obtain an accurate weight. If the baby is wearing a diaper, the diaper should be removed. If any heavy clothes remain on the child, make a note in the Notes section. Seca 874 Scale

- 1) Remove scale from bag.
- 2) Be sure that the scale is placed on a flat, hard, even surface. All 4 legs of the scale should make contact with the ground surface, without wobbling. It may be helpful to place a piece of plywood on the ground underneath the scale.
- 3) When batt appears in the display, you should change the batteries. Remove the old batteries and insert 6 new batteries.

Turn the power on the scale when you are ready to begin weighing. If the child is unable to stand on the scale, you will use the 2 in 1 weighing function (called tared weighing). The 2 in 1 function enables the weight of babies and small children to be determined while an adult holds them. Identify a suitable area that is flat for horizontal placement of the scale. Press the start key with no load on the scale. The scale is ready for use when it sets to 0.00. If necessary, switch the weight display to KG: hold down the 2 in 1 key for about 3 seconds. Press the start key with no load on the scale. Wait until the display shows 0.00. Ask the adult to remove his/her shoes and stand in the middle of the scale without the child. S/he should remove any long garments, as these can cover the display and also lead to variable measurements. After the adult's weight appears on the display, tell him/her to remain standing on the scale. Press the 2 in 1 key to activate the function. The scale stores the weight of the adult and the display returns to zero. When 0.00 and NET appear in the display, hand the child to the adult. The scale will determine the weight of the child. Once the value is stable for about 3 seconds, the weight is measured.

Note: If an adult is very heavy (e.g. more than 100 kg) and the baby's weight is relatively low (e.g. less than 2.5 kg), the baby's weight may not register on the scale. In such cases, have a lighter person hold the baby on the scale.

The positioner will clearly call out the child's weight to the recorder. Record the child's weight to the nearest 0.01 kg. Repeat the measurement 2 more times. Note that only the baby needs to removed from the scale; the adult should remain on the scale the entire time. To turn off the 2 in 1 function, press the 2 in 1 key. The 2 in 1 function remains on until you press the 2 in 1 key again, or until the scale switches off automatically. If several children are to be weighed consecutively with the same adult holding the babies, it is important that this person's weight does not change (e.g. due to a piece of clothing being removed/added). If the child is able to stand on the scale, you will weigh the child alone. Talk with the child about the need to stand still. Communicate with the child in a sensitive, non-frightening way. Press

the start key with no load on the scale. The scale is ready for use when it sets to 0.00. Ask the child to stand in the middle of the scale. Once on the scale, the child must stand still. The HOLD function is automatically activated for weights over 1.5 kg/3.3 lbs. The display flashes until a stable weight has been measured. The display is then frozen until the next weighing operation.

Note: If the child jumps on the scale or won't stand still, you will need to use the tared weighing procedure instead.

The positioner will clearly call out the child's weight to the recorder. Record the child's weight to the nearest 0.01 kg. Repeat the measurement 2 more times. Have the child move completely off the scale and then stand again on the scale. If no further weighing operations are performed, the scale switches off automatically after 2-3 minutes.

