8.4.1 Scale Calibration

In order to monitor the calibration of the scales over time, each team will weigh a 5 kg test weight at the beginning and end of the day. This measurement will take place at the site of the scale storage so that the weights do not need to be carried to the field. In some cases, these weights will be kept in a project vehicle.

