- weight gain Defined as grams per kilogram per day (g/kg/day) will be compared between arms separately at days 14 and 180 using linear regression. Baseline weight is accounted for in our metric of weight gain and will not be included in the regression analysis. We will use ordinary least squares method of estimatation and permutation tests to estimate coefficient p-values.
- HAZ, WAZ, WHZ, MUAC As secondary analysis, we will perform separate ANCOVA of anthropometric indicators at days 14 and 180, adjusting for baseline.

3 Sample Size Considerations

We assume a mean (standard deviation) alpha Shannon's index of 16.47 (7.12) using results from Thuy et al. [DAR⁺17]. Assuming 80% power and detectable effect size of 1.02 standard deviations and no loss to follow-up, we propose a sample size of 225 per group, totaling 450 study participants.

4 Randomization

The randomization will be conducted using R. The function sample with option replace=FALSE will be used to conduct the random shuffling. Note that the choice of the random number seed completely determines the randomization. To ensure the integrity of the randomization, we will use the procedure we used for MORDOR/Malawi.

Samples will be randomly grouped into 5-pools for processing, within an arm and a time point.

5 Abbreviations

ANCOVA Analysis of covariance

- $\mathbf{DSMC}\,$ Data and Safety Monitoring Committee
- ${\bf HAZ}$ height for age Z score
- MUAC Mid upper arm circumference
- ${\bf SAP}\,$ Statistical Analysis Plan
- \mathbf{WAZ} weight for age Z score
- \mathbf{WHZ} weight for height Z score

References

[DAR⁺17] T. Doan, A. M. Arzika, K. J. Ray, S. Y. Cotter, J. Kim, R. Maliki, and et al. Gut microbial diversity in antibiotic-naive children after systemic antibiotic exposure: A randomized controlled trial. *Clinical Infectious Disease*, 64, 2017.

6 Revision History

- 29 May 2019 Revised specification and wording of primary and secondary outcomes. Moved weight gain to secondary outcome. Clarified Bonferroni correction for certain species.
- 13 Jan 2020 Updated the pre-specified sample size for the sub-section of GAMIN sample (GAMIN QOD).
- 16 Jan 2020 Abbreviated the study name on title page.
- 20 Mar 2020 Added sample size considerations section and specification of day 180 time window.
- 08 May 2020 Specified WHO standard range for inclusion for anthropometric (child growth) analysis.
- 02 Jul 2020 Increased upper range of day 180 window from day 210 to day 240.

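### The three 2-in-1 weights of a held child share one stored tare, so repeating the reading does not average out the tare error (minor; noise only)

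*Protocol*

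**What the plan says.** Protocol 9.4 (Measuring Weight) has two procedures.

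- **Held children.** A child who cannot stand, or will not stand still, is weighed with the 2-in-1 function. The adult steps on alone and the key is pressed: "The scale stores the weight of the adult and the display returns to zero". The child is then handed over and the net weight is read. The operator is told: "Repeat the measurement 2 more times". The accompanying instruction is: "Note that only the baby needs to removed from the scale; the adult should remain on the scale the entire time". On how long the stored weight lasts: "The 2 in 1 function remains on until you press the 2 in 1 key again, or until the scale switches off automatically". No step clears it between readings. The section also foresees one adult serving several children ("If several children are to be weighed consecutively with the same adult holding the babies") and there asks only that the adult's weight stay the same.
- **Standing children.** They are weighed alone, and for each repeat: "Have the child move completely off the scale and then stand again on the scale".

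The calibration section (numbered 8.4.1, within Chapter 9) says that "each team will weigh a 5 kg test weight at the beginning and end of the day". It does not mention 2-in-1 mode or an adult on the scale.

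In SAP 2.1.1, under secondary analyses, weight gain in g/kg/day "will be compared between arms separately at days 14 and 180 using linear regression". WAZ and WHZ, which also depend on weight, are analysed by ANCOVA at the same visits. Neither document gives a weighing-error SD or says how the three readings are combined.

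**The concern.** Repeat readings are worth taking because independent errors shrink when combined. In 2-in-1 mode each net weight is a gross reading minus the stored adult weight. Only the gross reading is repeated. A random error in the stored weight, for example from sway while it was captured, enters all three net weights with the same sign and size. The three can agree closely and still be wrong together. Standing children have no tare and step fully off each time, so the lightest children get the weaker repeat.

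Day-14 weight gain is sensitive to this. It is a small difference between two weights, divided by a small body weight and by 14 days. The error enters at both visits and is largest per kilogram in the youngest children. What is at stake is precision in a secondary outcome, when the protocol already spends the time on three readings.

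**Working it through.** The plan states no weight-error figure, so there is nothing to reproduce. The check is a variance calculation with labelled assumptions.

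**From the documents:** three readings per child; one stored tare for all three (Protocol 9.4); weight gain in g/kg/day at day 14 (SAP 2.1.1).

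**Assumed, because the documents are silent:** the mean of three is used; the reading SD is s; the tare variance is r·s²; tare and reading errors are independent of each other and between visits; and re-taring gives a fresh, independent tare error.

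**Step 1. Ratio of error variances.**
- One shared tare: s²(r + 1/3). The tare term is not divided by 3.
- A new tare each time: s²(1 + r)/3.
- Ratio: (1 + 3r)/(1 + r).

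| r | 0 | 0.1 | 0.25 | 0.5 | 1 | 2 | 4 | limit |
|---|---|---|---|---|---|---|---|---|
| Ratio | 1.00 | 1.18 | 1.40 | 1.67 | 2.00 | 2.33 | 2.60 | 3.00 |

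Simulation with 400,000 draws agrees (2.01 at r = 1, 1.40 at r = 0.25). With the median instead of the mean, the simulated ratio is 1.62 at r = 1 and 1.25 at r = 0.25.

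**Step 2. Error SD of day-14 weight gain.** SD = √(2·Var)/(W·14), treating the baseline weight in the denominator as fixed. Take s = 50 g, r = 1 and W = 6 kg, so W·14 = 84:
- Shared tare: Var = 1.333 × 2500 = 3333 g²; √6667/84 = 0.97 g/kg/day.
- Re-tared: Var = 0.667 × 2500 = 1667 g²; √3333/84 = 0.69 g/kg/day.

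**Step 3. Share of outcome variance saved by re-taring.** With a true between-child SD of σ, the saving is (0.945 − 0.472)/(σ² + 0.945), where 0.945 and 0.472 are the squares of the unrounded SDs in Step 2. The same formula gives the other rows.

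| Assumptions | σ = 2 | σ = 4 |
|---|---|---|
| 6 kg, s = 50 g, r = 1 | 9.6% | 2.8% |
| 6 kg, s = 50 g, r = 0.25 | 2.7% | 0.7% |
| 6 kg, s = 10 g, r = 1 | 0.5% | 0.1% |
| 4 kg, s = 50 g, r = 1 | 17.4% | 5.9% |

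**Step 4. Effect on the confidence interval.** A variance saving of 2.8-9.6% shortens an interval by 1 − √(1 − 0.028) = 1.4% to 1 − √(1 − 0.096) = 4.9%, among held children. If half of all children were held (assumed) and the rest had the same outcome variance, the trial-wide saving would be 1.4-4.8% of variance, or 0.7-2.4% of interval width.

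**Day 180.** The divisor is 180 days instead of 14, so the same weighing error is 14/180, about 0.08, of its day-14 size in g/kg/day.

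**The case against.** The strongest reply is that this is a small matter of technique and that 9.4 already guards against tare error. The adult removes shoes and long garments, the value must be stable for about 3 seconds, the holder's weight must not change, and a lighter person holds a very small baby if the weight may not register. These controls are real and make a small tare error plausible. An adult standing alone may well be steadier than an adult holding a moving infant, which puts r below 1. The 50 g used above is five times the 0.01 kg recording unit and has no basis in the documents. All of this stands, and it limits the size. It does not make the repeats independent, because every control acts on a tare that is still captured only once.

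Readers might infer more than the text supports in four ways:

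- **That the error variance is simply doubled.** This needs r = 1 and a mean of three, and the documents state neither.
- **That the adult staying on the scale is the cause.** The direct cause is that the function is not reset. The tare could be re-stored with the adult still in place.
- **That the arms are biased.** Children are individually randomized, staff and families are masked, and the procedure is the same in both arms.
- **That a 5 kg check in 2-in-1 mode would settle the registration problem.** The note in 9.4 gives as its example an adult above 100 kg with a baby below 2.5 kg, and a 5 kg weight does not test that.

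Timing also counts. Protocol 4.6 dates baseline testing of 407 + 43 = 450 children to November 2019 and day-14 visits to December 2019. New wording cannot change those weights.

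**Conclusion.** The structural point holds without any assumed number: the three weights of a held child share one tare, and neither a mean nor a median removes its error. The size is conditional. The error variance is 1 to 3 times that with re-taring, and exactly 2 only if tare and reading errors are equally variable and the mean is used.

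In practice this is modest extra noise in weight gain, WAZ and WHZ for held children only; the WAZ and WHZ effects were not calculated. Under the assumptions above it is about 3-10% of day-14 weight-gain variance at 6 kg with s = 50 g and r = 1, more in a 4 kg infant, and under 1% at 6 kg if s is near 10 g. The microbiome outcomes and the sample size do not depend on it. Severity: minor.

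**What to change.** In Protocol 9.4, for 2-in-1 weighing, require the stored adult weight to be cleared and stored again before each of the three readings and for each new child. Having the adult step off and re-zeroing the scale each time is preferable, because it makes the repeat fully independent, but it is not essential. Amend the sentence that keeps the adult on the scale throughout so that it fits the new step. State, in the Protocol or the SAP, how the three readings are combined.

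For weights already taken, report the shared tare as a limitation of the weight-based outcomes. The new wording helps only weighings still to come, or later use of the procedure.

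A daily 2-in-1 check with the existing 5 kg weight and an adult on the scale is optional. It would show whether tared weighing works under adult load, but not whether a very small baby registers.

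Cost: a few lines of text and about a minute or less per held child per visit, with no new equipment or staff.
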